1) Group B experienced larger improvement in coagulopathy as measured by fibrinolysis from Field to ED (one of our secondary objectives, see below): as demonstrated by a repeated measures mixed linear model, the interaction between time and randomization approached significance, suggesting that group assignment modified the temporal trends of fibrinolysis as

measured by rTEG Ly30. Limiting the model to patients who presented in the Field in severe shock further increased the significance.

Linear Models for Repeated	ear Models for Repeated Measures including only Field and ED times for TEGs											
Model for LY30		ALL PATIE	ENTS		SEVERE SHOCK ONLY (Field SBP<=70mmHg)							
	Beta	SE	P-VALUE	Beta	SE	P-VALUE						
Intercept	6.7484	2.8959		6.2593	3.7915							
Time (ED, Field)	1.5018	2.9601	0.2528	4.9843	4.1149	0.5087						
Randomization (groups A, B)	3.3722	4.165	0.8321	7.0309	5.9547	0.9767						
Randomization*time (Interaction)	-8.1625	4.4787	0.0721	-14.3628	6.5971	0.0348						

2) Toleration of longer time to RBC **without** any adverse event, which was another of our secondary objectives (an objective of major importance to the military, and consequently to our funder, the Dept. of Defense)

There seemed to be a difference in time from injury and from ED arrival to the first required RBC favoring group B, who tolerated longer time without increasing mortality or any other adverse event. A survival analysis, however, did not reach significance.

More important, there has been no increase in adverse events or any suggestion of harm to enrollees and enrollment has been on target.

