- a. **Blunt trauma mechanism:** There is evidence to suggest that the coagulation and inflammatory responses to injury differ by trauma mechanism, as they cause different tissue damage.^{101, 102}
 - 1. **Hypothesis:** Blunt trauma patients will have different effect sizes than penetrating trauma victims regarding the primary endpoint and secondary endpoints
 - 2. **Statistical tests:** Same tests described for primary and secondary endpoints stratified by mechanism of injury (blunt vs. penetrating). We will compare the 95% confidence intervals to determine overlap between the blunt and penetrating groups for each endpoint.
- b. Absence vs. presence of serious traumatic brain injury (TBI): there is evidence to suggest a differential coagulation and inflammatory response by the presence of TBI.^{101, 103, 104}
 - Hypothesis: Patients with associated TBI (defined as Abbreviated Injury Score, AIS, for Head >3) will have different effect sizes than their counterparts without TBI regarding the primary endpoint and secondary endpoints.
 - Statistical tests: Same tests described for primary and secondary endpoints stratified by presence of TBI. We will compare the 95% confidence intervals to determine overlap between the two groups for each endpoint.
- c. Presence of very severe hemorrhagic shock (HS, defined as SBP≤70 mmHg) versus severe HS (defined as SBP 71-90mmHg + Heart rate>=108bpm): There is evidence that the patients with very severe HS shock are more likely to require massive transfusion and present severe coagulopathy, thus potentially having differential mortality.¹⁰⁵
 - Hypothesis: Patients with very severe hemorrhagic shock (defined as SBP≤70mmHg) will have different effect sizes than their counterparts with severe hemorrhagic shock (defined as SBP 71-90mmHg +heart rate>=108bpm) regarding the primary endpoint and secondary endpoints.
 - Statistical tests: Same tests described for primary and secondary endpoints stratified by degree of hemorrhagic shock. We will compare the 95% confidence intervals to determine overlap between the two groups for each endpoint. Overall experiment error will be adjusted for the number of subgroups being analyzed using the Bonferroni method.

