- 1. Assessing Phase 2 trial results for promising benefits of the therapy: Because the trial has low power for the primary endpoint and some of the secondary endpoints, it is unlikely that we can detect a statistical significant difference. Thus, it is important to pre-determine the findings that we believe will indicate promising results that must be further investigated in larger Phase 3 trials. We will specifically look at the following measures to declare that the therapy is promising:
 - a. Statistical significant difference in primary endpoint or secondary endpoints
 - b. Strong, yet not statistically significant association (e.g., p-value = 0.10 to 0.05) with improved primary and secondary endpoints. The direction

of the association must indicate therapy benefit in ALL primary and secondary endpoints. Associations indicating harm will be reviewed by the DSMB for possible early termination.

c. Exploratory analyses of variables with supporting evidence for association with improved patient outcomes with statistically significant results (respecting the boundaries determined by the interim analyses methods, and adjusted for multiple comparisons as detailed in the description of the exploratory analyses).

The DSMB will also be in charge to making recommendations regarding the promising nature of the therapy and whether Phase 3 trials are warranted.

2. Interrupting the trial early:

The DSMB will be responsible for making a recommendation for early stopping of the trial. The DSMB will be asked to address early termination during each and every time they are activated, as described in the DSMB roles and responsibilities. In brief, the DSMB will be activated in case of a unanticipated problem, or during the interim analyses. Drs. [name] and [name] will prepare the materials for DSMB review containing:

- a. blinded results (experimental and control groups will be referred as A and B) of effectiveness of randomization, primary and secondary outcomes, as well as exploratory analyses (most especially the two subgroup analyses regarding blunt versus penetrating mechanism, presence of traumatic brain injury and Field SBP≤70mmHg versus SBP 71-90mmHg), any potential adverse events, and missing data description (to include number missing and their characteristics regarding outcomes and covariates).

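### The subgroup Bonferroni correction in IV.G.2 counts subgroups but not the 5 endpoints (8 hypotheses) tested in each, so it does not control the experiment-wise error that IV.I.1.c relies on

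*Combined protocol and SAP*

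**What the plan says.** IV.G.2 lists three pre-planned subgroup factors: (a) blunt versus penetrating mechanism, (b) serious traumatic brain injury, and (c) degree of hemorrhagic shock. Each has a hypothesis that effects differ between strata across all main endpoints. For mechanism it reads "Blunt trauma patients will have different effect sizes than penetrating trauma victims regarding the primary endpoint and secondary endpoints".

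Each factor has two analysis steps. The endpoint tests are repeated within strata (for shock, "Same tests described for primary and secondary endpoints stratified by degree of hemorrhagic shock"). The strata are then compared by interval overlap (for mechanism, "We will compare the 95% confidence intervals to determine overlap between the blunt and penetrating groups for each endpoint").

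The multiplicity sentence, "Overall experiment error will be adjusted for the number of subgroups being analyzed using the Bonferroni method", appears once, at the end of item c. It gives no number for the divisor and no target error rate.

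Two later sections use the results. IV.I.1.c accepts statistically significant exploratory findings as evidence of promise, "respecting the boundaries determined by the interim analyses methods, and adjusted for multiple comparisons as detailed in the description of the exploratory analyses". IV.I.2.a sends subgroup results to the DSMB, "most especially the two subgroup analyses regarding blunt versus penetrating mechanism, presence of traumatic brain injury and Field SBP≤70mmHg versus SBP 71-90mmHg".

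**The concern.** A Bonferroni correction controls error over a family only if the divisor is at least the number of tests in that family. Here each subgroup factor is crossed with every primary and secondary hypothesis, and the divisor ignores that second dimension. IV.G.4 shows that the plan can handle two dimensions: there Bonferroni covers the number of coagulation parameters and Tukey's method covers the time points within each.

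The divisor itself is also undefined. IV.G.2 has three factors (six strata), IV.I.2.a says two and then names three, and the sentence sits under item c only.

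What is at stake is the label. IV.I.1 concedes that significance on the primary endpoint is unlikely, so the exploratory route matters. Under IV.I.1.c a chance subgroup finding could be presented as multiplicity-adjusted evidence for Phase 3.

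**Working it through.** **1. Count the family.** The hypotheses in IV.E and IV.F are:
- 28-day mortality (1);
- the composite of in-hospital death or multiple organ failure (1);
- mean INR and INR>1.5 (2);
- mean TEG G and G>5.0 (2);
- base deficit and lactate (2).

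That is 5 endpoints and 8 hypotheses. Between-stratum comparisons number 3 × 8 = 24 (3 × 5 = 15 if only endpoints are counted). Within-stratum tests number 6 × 8 = 48 (or 6 × 5 = 30).

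**2. Base alpha.** The plan states no error rate for the subgroup family, so there is no figure to reproduce. I take 0.05 two-sided from IV.E. Integrating the printed boundaries returns a total alpha of 0.0500 for both the three-look and the five-look tables.

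**3. p-value tests, independence.** With divisor k and m tests, the family-wise error is 1 − (1 − 0.05/k)^m, with upper bound m × 0.05/k.

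| Reading | k | m | Independent | Upper bound |
|---|---|---|---|---|
| Between strata, 5 endpoints | 3 | 15 | 22.3% | 25% |
| Between strata, 8 hypotheses | 3 | 24 | 33.2% | 40% |
| Within strata, 8 hypotheses | 6 | 48 | 33.1% | 40% |
| Within strata, 8 hypotheses | 3 | 48 | 55.4% | 80% |

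**4. p-value tests, correlated endpoints.** The documents give neither endpoint correlations nor subgroup prevalences. Assumptions:
- 8 equicorrelated endpoint Z-scores, correlation ρ;
- penetrating injury 50%, brain injury 25%, SBP≤70 mmHg 50%, factors independent;
- no treatment effect anywhere, and a single analysis.

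The stratum Z is the information-weighted sum of its cells. The interaction Z is the stratum difference over its standard error. Error is P(max|Z| > z at 0.025/k), from 100,000 simulations.

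| Test | k | ρ=0.8 | ρ=0.5 | ρ=0.2 |
|---|---|---|---|---|
| Within stratum | 3 | 25% | 38% | 47% |
| Within stratum | 6 | 15% | 23% | 28% |
| Interaction | 3 | 17% | 26% | 32% |
| Interaction | 6 | 9.5% | 15% | 18% |

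Divisor 2, the literal count in IV.I.2.a, gives 50% (within stratum) and 36% (interaction) at ρ=0.5.

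**5. The plan's overlap rule.** Two intervals fail to overlap when the difference exceeds z(SE₁+SE₂). With R the ratio of standard errors, the per-comparison error is 2[1 − Φ(z(1+R)/√(1+R²))].
- Literal 95% intervals, R=1: 2[1 − Φ(1.96 × 1.414)] = 0.56%. Over 24 independent comparisons: 1 − (1 − 0.00557)^24 = 12.6%.
- Intervals widened to 98.33% (divisor 3), R=1: 0.071% per comparison, 1.7% over 24.
- More unequal strata: R=3 gives 27% (95% intervals) or 5.7% (98.33% intervals) over 24.

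Under the assumptions of step 4:

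| Intervals | ρ=0.8 | ρ=0.5 | ρ=0.2 |
|---|---|---|---|
| Literal 95% | 7% | 11% | 14% |
| Widened, divisor 3 | 1.2% | 1.7% | 2.0% |
| Widened, divisor 6 | 0.4% | 0.5% | 0.5% |

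**6. Corrected divisors.** Three interaction tests at 0.05/3 = 0.0167 give 1 − (1 − 0.0167)³ = 4.9% if independent, and at most 5%. All 24 at 0.05/24 = 0.0021 give 4.9% if independent, and about 3-5% under step 4.

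**The case against.** The strongest reply is that the plan does not call for an interaction Z-test. Its stated criterion for a subgroup difference is interval overlap, which is conservative per comparison. If the Bonferroni step widens those intervals, the error stays at about 2% or less with all eight hypotheses counted. This stands, and it limits the point: the larger percentages apply only to judgement by p-value. It does not remove the point. The text says 95% intervals and never says they are widened, the repeated endpoint tests produce within-stratum p-values, and IV.I.1.c speaks of statistical significance.

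The section is also labelled exploratory, a promising result leads only to further study, and the DSMB weighs several inputs. That limits the consequence. But the plan chose to adjust this error and then relies on the adjustment.

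A reader might infer two stronger things:
- **That the subgroup error is simply some 15-38% against a promised 5%.** The documents do not support this. They state no target for this family, the 5% is carried over from IV.E, and any single range mixes tests, divisors and assumed correlations.
- **That the November 2016 addendum in IV.E already shows the failure, because it says "Limiting the model to patients who presented in the Field in severe shock further increased the significance" of a result with p=0.0348.** That result is a randomization-by-time interaction for LY30 within one stratum. LY30 is not among the eight hypotheses, and the analysis does not compare strata. It lies outside this family and is not evidence here.

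**Conclusion.** The concern holds in a limited form. The IV.G.2 correction omits the endpoint dimension and leaves its divisor undefined, so it does not deliver the adjusted significance that IV.I.1.c presupposes. The size depends on the decision rule, which the plan leaves open: well above 5% on every p-value reading, moderately above it for literal 95% interval overlap, and below it if the intervals are widened.

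These sizes rest on the assumed correlations and prevalences, the inferred 5% target and a single analysis. Fisher's exact test would lower the rates for the binary primary and composite endpoints, and repeated DSMB looks could raise them. The point deserves correction because a stated rule relies on it. It does not bear on the primary analysis.

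**What to change.** In IV.G.2:
- Move the multiplicity sentence so that it covers items a, b and c.
- Replace the interval-overlap rule with a treatment-by-subgroup interaction test.
- Define the adjusted family as the three interaction tests on 28-day mortality, each at 0.05/3.
- Label within-stratum tests, and subgroup results on all other endpoints, as descriptive and not eligible for IV.I.1.c.

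If the sponsor wants all outcomes kept in the adjusted family, use 0.05/24 = 0.0021 for the interaction tests instead. In IV.I.2.a, correct the count of subgroup analyses from two to three; this is clerical.

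The cost is wording only, with no change to conduct, data or sample size. The downside is that subgroup findings on laboratory endpoints lose any claim to adjusted significance.

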- **1. Data Collection:** Each patient enrolled will be given a unique patient identifier that will be kept in a separate database to protect heath information.
 - a. Laboratory studies will be performed to evaluate the acute coagulopathy of trauma from blood samples collected in the field, upon ED arrival, at 2, 4, 6, 12, 24, 48 and 72 hours, and day 5 and day 7 post-injury as shown below in the figure titled "Biological Sampling and Study Timeline." Standard coagulation assays (prothrombin time/INR, activated partial thromboplastin time, fibrinogen levels, and platelet counts), ROTEM (rotational theomboelastography) and TEGs, [rapid, tissue factor-activated thrombelastograms (r-TEG), classic kaolin-activated TEGs with platelet mapping of the response to arachidonic acid (AA) and adenosine di-phosphate (ADP)] will all be completed in the Clinical Laboratories or Trauma Research Laboratory at Denver Health Medical Center in addition to CBC, serum chemistries, hepatic profile, lactate, and arterial blood gases. Crystalloid volume, resuscitation fluids and number of blood products infused will be recorded hourly.
 - b. In the event that multiple patients are enrolled in the study at the same time, due to logistical restrictions, samples may be delayed or not collected. Sample collection and processing will be resumed according to the protocol at the earliest opportunity.
 - c. The clinical data both at presentation and throughout hospitalization will be obtained and recorded in the COMBAT/Trauma Activation Database. Additional clinical information specific to the study including blood product transfusion will be recorded in the REDCap data collecting system. Clinical data entered will include a summary of injuries on admission, illness during the index admission, medical history, medications, and infectious and non-infectious complications as well as time and cause of death. Patient data entry will end with the index hospital stay. Outpatient information will not be included.
 - d. Patients will be contacted after hospital discharge on day 28 primarily for 28-day mortality.
 - e.Each field, ED arrival, 2, 4, 6, 12, 24, 48, 72 hour, day 5 and day 7 time point blood samples obtained will be banked by a unique patient identifier for further research and for determination of proteomics and

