- 7. Waveform Data: We would like to collect more CRI data from very sick individuals to see how the algorithm captures their clinical presentation and resuscitation. We also want to see if a certain minimal CRI or low CRI for a period time triggers the acute coagulopathy of trauma. Just as other vital signs can be used to indicate certain medical conditions, we would analyze the data to see if the acute coagulopathy of trauma correlates with either a minimal CRI or low CRI for a certain period of time. We will also collate the CRI data with the clinical timeline of interventions, medications and fluids given. This will help us correlate the effects of the interventions, medications and fluids with changes in CRI.
 - a. Data analytics will be used to analyze the waveform data in relation to fluid resuscitation types, rates and volumes, response to fluid therapy, types of injuries, operative timing and management, length of ICU and hospital stay, as well as overall outcomes. We will compare the waveform features from trauma patients to those features collected from research subjects with analogous levels of LBNP applied.

E. Primary Study Objectives and Endpoints

 Primary Study Objective: to determine the efficacy, as measured by 28-day mortality reduction, of using postinjury field-resuscitation with plasma first compared to standard of care (SOC).

Primary Endpoint: 28-day mortality

a. **Definition:** 28-day mortality is defined as death within 28 days post injury (death of any cause except for death due to a second, clearly unrelated traumatic injury suffered after discharge). Research coordinators will verify the vital status of all patients at day 28. Patients

discharged home before day 28 will be reached using contact information obtained at discharge. In case of transfer or discharge to another facility before day 28, research coordinators will coordinate with the other facility to ascertain vital status, verify contact information at discharge or determine patient disposition at day 28 postinjury

- b. **Hypothesis**: 28-day mortality will be significantly higher^{*} in control patients compared to experimental patients.

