- **3.** Adverse-outcome free days: There is ample evidence suggesting a strong association with these outcomes and mortality. These outcomes were devised by the ARDS Net group to overcome survivor bias, initially for mechanical ventilation and quickly expanded to include other outcomes potentially biased by survivorship. Outcome-free-days (OFD) as proposed by the NIH sponsored ARDSnet trials,¹⁰⁶ takes the observation time into account. We apologize for not providing more information on this measure; we assumed the reviewers were familiar with it as it is so often used in recent clinical trials. Indeed, ALI-free days, MOF-free days and ventilator-free days (VFD) were proposed exactly to deal with the survivor –bias stated by the reviewers.
 - a. Definition: VFDs can be arbitrarily defined as the number of days between successful weaning from mechanical ventilation and day 28 after study enrollment. The 28-day landmark was suggested both because interventional trials in acute lung injury typically involve a 28day treatment/follow-up period after the patient enrolls in the trial and because most, but not all, patients with acute lung injury have either died or been successfully weaned from mechanical ventilation by day 28. VFDs are defined as follows:

VFDs = 0: If the patient dies before 28 days.

VFDs = (28 - x): If the patient is successfully weaned from mechanical ventilation within 28 days, where x is the number of days spent receiving mechanical ventilation.

VFDs = 0: If the patient requires mechanical ventilation for 28 days or more.

For example, VFD=2 means that the patient spent at least 26 days on the ventilator or, less likely, died within 2 days without being on a ventilator, both of which are considered poor outcomes.

- b. We will assess two adverse-outcome-free days measured over 28 days, as follows:
 - 1. Ventilation free days
 - 2. Acute Lung Injury (ALI) free days (as defined by the validated Denver Lung Dysfunction score)
- c. **Hypothesis:** Experimental group patients will have longer ⁺⁺⁺adverseoutcome-free-days than control patients.

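### The ventilator-free-day example contradicts its own scoring rule, and no ventilator or lung data are scheduled after transfer to complete a 28-day count

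*Combined protocol and SAP*

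**What the plan says.** Section IV.G.3.a (Adverse-outcome free days, Definition) gives three scoring lines:

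- Death: "VFDs = 0: If the patient dies before 28 days".
- Successful weaning within 28 days: 28 - x, "where x is the number of days spent receiving mechanical ventilation".
- Prolonged ventilation: "VFDs = 0: If the patient requires mechanical ventilation for 28 days or more".

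The worked example follows. It says that "VFD=2 means that the patient spent at least 26 days on the ventilator" and then adds "or, less likely, died within 2 days without being on a ventilator, both of which are considered poor outcomes".

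Section IV.G.3.b sets the window: "We will assess two adverse-outcome-free days measured over 28 days, as follows". The two outcomes are ventilation-free days and ALI-free days. The second is defined through the Denver lung dysfunction score and has no scoring formula of its own.

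On data collection, section IV.C.1.c says: "Patient data entry will end with the index hospital stay. Outpatient information will not be included". Section IV.C.1.d describes the day-28 contact as being mainly for mortality. For patients transferred or discharged to another facility before day 28, the primary endpoint definition in section IV.E says that "research coordinators will coordinate with the other facility to ascertain vital status", and it also mentions verifying contact information or determining disposition at day 28. The consent procedure in section IV.M.1.d seeks agreement to collect clinical data up to day 28.

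Section IV.H gives missing-data rules for mortality, the secondary endpoints, the variables used to check randomization, and 24-hour mortality. It gives none for the outcome-free days.

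**The concern.** There are two separate problems in the same endpoint.

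First, the rule and the example give different scores to the same patient. Section IV.G.3 says these outcomes were chosen to deal with survivor bias, and scoring every death as 0 is what provides that protection. An example that gives an early death a positive score points the other way. Because ALI-free days have no formula of their own, whoever programs them must borrow from this text.

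Second, a 28-day count needs ventilator and lung status to day 28, or a stated convention for the days that are not observed. The plan has neither for a patient who leaves the index hospital still ventilated. The gap can also go unnoticed. If x is filled with index-stay ventilator days, the record looks complete, and the general missing-data provision in section IV.D.1 is never triggered.

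The stakes are limited but not nil. Aim 3 in section I includes reducing acute lung injury. Section IV.I.1.c lets statistically significant exploratory results, adjusted for multiplicity, support calling the therapy promising. Section IV.I.2 sends exploratory analyses to the DSMB. Treatment is not blinded, so the scoring convention should be fixed in writing before it is needed.

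**Working it through.** **1. The example against the rule.** The inputs are the three scoring lines and the example in section IV.G.3.a. The third column is not in the plan. It is shown because it is the variant, among those tried, that yields the example's 2 for the early death.

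| Patient | Score under the written rule | Days alive and off the ventilator |
|---|---|---|
| Alive, 26 ventilator days | 28 - 26 = 2 | 2 |
| Alive, 27 ventilator days | 28 - 27 = 1 | 1 |
| Alive, 28 ventilator days | 0 | 0 |
| Died day 2, never ventilated | 0 | 2 - 0 = 2 |

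The example's 2 is reproduced for a survivor with exactly 26 ventilator days. It is not reproduced for more than 26 days, nor for the early death. Ignoring death and using 28 - x would give that patient 28 - 0 = 28, which is not 2 either.

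*Size.* The documents give no count of never-ventilated early deaths. If an assumed 3% to 12% of an arm were scored 2 instead of 0, the arm mean would rise by 0.03 x 2 = 0.06 to 0.12 x 2 = 0.24 days. As an extreme case, suppose every death were so scored at the second-interim mortality of 12% and 13% (section IV.E, Addendum of November 16, 2016). The difference between arms would then move by (0.13 - 0.12) x 2 = 0.02 days.

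**2. What is collected against what is needed.**

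- Needed: ventilator and lung status through day 28 (IV.G.3.b).
- Collected: clinical data to the end of the index stay (IV.C.1.c).
- Named after that: vital status, contact information and disposition (IV.C.1.d; IV.E, primary endpoint definition).
- Permitted by consent: clinical data to day 28 (IV.M.1.d), but no section schedules ventilator or lung data after transfer.

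A patient still ventilated at transfer before day 28, and alive at day 28, has not been observed to be weaned. The condition for 28 - x is therefore not shown to be met, and neither is the condition for 0. The score is undetermined.

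*Size if index-stay days are used as x.* Let t be the transfer day, and assume ventilation from the start through t. The truncated score is 28 - t. The true score lies between 0 and 28 - t, so the overstatement is at most 28 - t.

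| Transfer day (illustrative) | Score from index-stay days | True score |
|---|---|---|
| 10 | 18 | 0 to 18 |
| 15 | 13 | 0 to 13 |
| 20 | 8 | 0 to 8 |

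With 112 patients per arm (same Addendum) and k day-10 transfers in one arm, that arm's mean rises by at most 18k/112:

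- k = 1: 0.16 days
- k = 3: 0.48 days
- k = 5: 0.80 days
- k = 10: 1.61 days

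The values of k are assumptions. The documents give no number.

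**The case against.** Several points on the other side stand.

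- The three scoring lines are introduced as the definition, and the example is only illustrative. A careful programmer would follow the lines, so the first problem is largely an editorial correction.
- A reader might infer that the plan itself scores a patient transferred on a ventilator as an early success, for example 28 - 14 = 14 for a day-14 transfer. It does not. The formula 28 - x is reserved for patients successfully weaned within 28 days. The score of 14 arises only if an analyst overlooks that condition.
- A reader might infer that the day-28 contact is restricted to mortality. The text says it is mainly for mortality, the transfer contact also covers disposition, and consent extends to clinical data up to day 28. Collection of other items is not forbidden.
- A reader might extend the example to a never-ventilated death on any day d scoring d, up to 27, and apply it to all 27 to 29 deaths expected among 224 patients at 12% to 13% mortality (0.12 x 224 = 26.9; 0.13 x 224 = 29.1). The example mentions only death within 2 days without ventilation and a score of 2, so the documents support neither figure.
- The group with a ventilator-day gap is narrow. Patients who stay to day 28, or whose death is ascertained, have none. Counting the days after discharge home as event-free is a reasonable convention, though the plan does not state it.
- ALI-free days are not wholly undefined. Section IV.N.8, Table 4 and the score table beneath it give a lung dysfunction threshold and grades, and the death rule would naturally carry over.

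These points reduce the size and tone of the concern. They do not remove the contradiction in section IV.G.3.a or supply the missing post-transfer data. Analysts cannot recover those data later if nobody asks for them.

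**Conclusion.** Both problems hold, in limited form. The example is wrong under the plan's own rule: the early unventilated death scores 0, not 2, and the ventilator branch should say 26 days. The data schedule leaves both 28-day counts undetermined for survivors transferred on a ventilator before day 28, and sections IV.C.1, IV.E, IV.G.3 and IV.M.1.d do not line up.

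For one patient, the possible overstatement is up to 28 minus the transfer day, if index-stay days are used as x. For an arm mean, it ranges from 0.16 to 1.61 days under the assumed 1 to 10 day-10 transfers among 112 patients. The effect of the example, as actually written, is a few tenths of a day at most under the assumed shares. The documents do not show how many patients either problem touches, so an actual distortion of the comparison between arms is possible but not demonstrated.

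The outcomes are exploratory. The primary endpoint and the listed secondary endpoints are unaffected. The correction is worth making because it is cheap and because exploratory results have a stated role in judging whether the therapy is promising.

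**What to change.** 1. In section IV.G.3.a, delete the death clause from the example and change the ventilator branch to 26 days. State that death before day 28 scores 0 for both ventilator-free and ALI-free days.
2. Align sections IV.C.1.c-d, IV.E (primary endpoint definition), IV.G.3 and IV.M.1.d. Exempt the 28-day outcomes from the index-stay stop, and record ventilator status and date of weaning at the contact with the receiving facility that is already planned.
3. Where these remain unknown, state that transfer on a ventilator is not successful weaning. Pre-specify one scoring convention, for example 0 days, and report index-stay days as a sensitivity analysis. State likewise how lung-score days after transfer or discharge are counted for ALI-free days.

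The cost is two extra data items at an existing contact and a few sentences of text. A score of 0 is pessimistic for patients weaned soon after transfer. Other conventions would also be acceptable if fixed in advance, and the sensitivity analysis shows how much the choice matters.
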